3.3.1. Study design

The proposed study is an observational, parallel group, non-randomized study in lactating mothers. It will be carried out at the University and Polytechnic Hospital La Fe (HULAFE), beginning at Month 21. Previously, the study protocol will be approved by the Ethics Committee for Biomedical Research of the Health Research Institute La Fe (Valencia, Spain) and the study participants will sign a relevant consent form. All procedures regarding volunteers' recruitment and participation, data security and handling will be in absolute accordance with the principles set under WP 9, concerning Ethical Requirements, and more specifically stated on Tasks 7.1 and 7.2 and D 7.2.

To address the objectives mentioned above, three mother-infant groups will be examined. In specific:

- Group A will consist of 25 pre-term infants fed with OMM (PT-OMM) and their mothers.
- Group B will consist of 25 pre-term infants fed with pasteurized DHM (PT-DHM), in range of complete enteral nutrition (150 mL/kg/day), and their mothers.
- Group C will consist of 25 full term infants receiving OMM (FT-OMM) and their mothers.

The study will be divided into two phases:

- A baseline phase, referring to the period between the time of delivery and the time preterm infants receive complete enteral nutrition (CEN) and full term infants recover of birth weight (RBW). During this period, all infants and their mothers will be evaluated, as described in the next section.
- 2. **An observational phase**, lasting six months and referring to the period that infants are fed with HMand/or formulas orsolid foods. During this period, assessments, as described below,

[figure not shown]

will be arranged for all mother-infants dyad and the donors providing the DHM in the hospital or the participants' home.

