3.3.2. Participants

Participants will be recruited in HULAFE. Visits at baseline, when preterm infants receive complete enteral nutrition (CEN; i.e. 150 mL/kg/day) and at months 1, 3, and 6 will be held at the hospital. Visits when full term infants recover of birth weight and at month 2 will be held at the participant's home.

The eligibility criteria for participating will be as follows:

Inclusion criteria

- Mother accepts to participate in the study and signs an informed consent form
- Gestational age < 32 weeks for the group of preterm infants and gestational age > 37 weeks for the full-term infants
- Exclusive consumption (i.e. >80% of intake) of OMM or DHM

Exclusion criteria:

- Mother requires special diet (e.g. celiac disease, diabetes)
- Mother consuming probiotics
- Infant needs intestinal surgery
- Severe congenital malformations
- Chromosomopathies

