Number of respiratory, gastrointestinal, and neurologic infections, number of hospital admissions due to infectious diseases as well as antibiotics use will be recorded for infants of all three groups upon every visit.

o Metabolome characterisation

For the characterization of metabolic profile urine samples will be collected from mothers of PT-OMM, PT-DHM and FT-OMM and their infants at each evaluation, as described in Deliverables 2.2 and 3.1.

Human milk nutrient composition assessment

OMM will be collected at every visit. DHM aliquots of each milk batch will be collected before and after pasteurization and fortification of DHM will be recorded. The detailed protocol is described in Deliverable 2.3.

Microbiome assessment

OMM and DHM before pasteurization will be analyzed for microorganism's content. Fecal samples from mothers of PT-OMM, PT-DHM and FT-OMM and their infants will be also collected for studying the microbiome at every visit. The protocol followed is described in Deliverable 2.1.

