3.3.5. Sample size

In order to achieve statistical power of at least 95% at 5% significance level of two-sided hypotheses for the evaluation of 10% standardized mean differences of fat and protein composition of HM, as well as growth markers (weight, height), and health status (number of gastrointestinal and respiratory diseases) of preterm infants, a total of 75 mother-infant dyads (25 per Group of Study II) will be enrolled.

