3.3.6. Statistical analysis

Associations between mothers' diet and HM composition will be examined with linear regression models. Associations with the macro- and micro-nutrients of the mothers' diet as the independent variable and HM macro- and micro-nutrient composition as dependent variable using prematurity, age and years of education as covariates, will also be examined using linear regression models. The analyses will be repeated separately from the groups of PT-OMM and FT-OMM. Furthermore, linear regression models will be performed with the HM macro- and micro-nutrient composition as the independent

variables and weight, length, cranial perimeter and number of diseases as the dependent using prematurity, age, years of education etc., as the covariates. The analyses will be repeated separately for the groups of preterm and full-term infants. Finally, composition of DHM in terms of nutrients and microorganisms content will be compared before and after pasteurization/storage using Student's t-test or Mann-Whitney test. The analyses will be performed by using STATA software (STATA Corp LLL, College Station, TX, USA).

Finally, additional statistical analysis with the view of deriving additional insights and influences in personalised nutrition will be presented in D2.5.

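### Study II fixes linear regression for the infant infection count, so its standard errors are not dependable; the open covariate list also does not name gestational age in weeks or birth size

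*Protocol*

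**What the plan says.** Protocol section 3.3.6 (Study II) states the method for infant outcomes in one sentence. Milk nutrient content is the predictor in a linear regression, with "weight, length, cranial perimeter and number of diseases as the dependent using prematurity, age, years of education etc., as the covariates". It continues: "The analyses will be repeated separately for the groups of preterm and full-term infants". One model type therefore covers three continuous growth measures and one count.

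Section 3.3.4.1 shows how the count arises, at every visit: "Number of respiratory, gastrointestinal, and neurologic infections, number of hospital admissions due to infectious diseases as well as antibiotics use will be recorded". Section 3.3.1 gives the observational phase as "lasting six months and referring to the period that infants are fed". Section 3.3.5 lists the count among the outcomes behind the sample size: "health status (number of gastrointestinal and respiratory diseases) of preterm infants".

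Section 3.3.2 separates the strata widely: "Gestational age < 32 weeks for the group of preterm infants and gestational age > 37 weeks for the full-term infants". Section 3.3.1 describes the study as non-randomised, with 25 dyads in each of three groups. Two of the groups are preterm (own mother's milk, donor milk) and one is full-term (own mother's milk).

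**The concern.** Ordinary linear regression takes its standard error from one residual variance shared by all infants. For a count, the variance normally grows with the mean. Two things follow.

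- **Pooled model.** If preterm infants have more infections, their residual variance is larger. The shared variance is then wrong for the slope whenever the milk component is spread differently in the two strata.
- **Within a stratum.** If milk composition is truly associated with infections, the mean and hence the variance change along the exposure. The standard error is then too small even without pooling, and a straight line can fit negative counts.

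Infections belong to objective c in section 3.2 (growth and other health parameters), and section 3.4 sends the associations into algorithm training. Misjudged precision would carry forward.

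The secondary concern is adjustment. A yes/no prematurity term is constant inside each stratum and drops out, leaving age and education as the named adjustment in the preterm infants. Feeding groups are not randomised, so differences in maturity or birth size between own-milk and donor-milk infants could confound the growth associations.

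**Working it through.** The protocol gives no figure for this analysis, so there is nothing to reproduce first. The power statement in section 3.3.5 is a separate matter and is not used here.

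**Inputs from the protocol:** 50 preterm and 25 full-term infants; linear regression; two-sided 5%.

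**Assumed inputs (not in the protocol):** mean counts, overdispersion, spread of milk exposure, strength of association, correlations.

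**1. Pooled model, no association, by hand.** Take mean counts of 1.5 (preterm) and 0.3 (full-term) with negative binomial dispersion 1, so variance = mean + mean²:
- preterm: 1.5 + 2.25 = 3.75
- full-term: 0.3 + 0.09 = 0.39

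The model uses the shared variance (50 × 3.75 + 25 × 0.39) / 75 = 2.63. The slope's true precision depends on the variance weighted by exposure spread s (preterm s = 1):

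(50 × 3.75 + 25 × s² × 0.39) / (50 + 25 × s²)

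The ratio of model to true standard error is √(2.63 / weighted variance), and rejection is about 2Φ(−1.96 × ratio).

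| Full-term spread s | Weighted variance | SE ratio | Approx. rejection | Simulated |
|---|---|---|---|---|
| 1 | 2.63 | 1.00 | 5.0% | 5.3% |
| 0.5 | 189.94 / 56.25 = 3.38 | 0.88 | 8.4% | 8.7% |
| 2 | 226.5 / 150 = 1.51 | 1.32 | 1.0% | 1.0% |

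Further simulation at these means gave 7.1-9.1% when preterm spread was 1.5 to 3 times larger, and 1.1-2.3% when full-term spread was 1.5 to 2 times larger. Other assumed rates (full-term mean 0.3 or 1.0, preterm three times that, Poisson or dispersion 1; 4,000 runs each) gave 4.3-5.6% with equal spread, 7.1-8.0% with full-term spread halved and 1.4-2.3% with it doubled. HC3 robust standard errors gave 3.0-5.5% in the pooled model.

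**2. Within strata, no association.** The variance is then constant inside the stratum, and simulated rejection was 4.7-5.7%.

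**3. True association in the 50 preterm infants** (same rates as the 4,000-run set):

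| Rate ratio per SD | Model SE / true SE | SE too small by | Runs with a negative fitted count |
|---|---|---|---|
| 1.5 | 0.79-0.89 | 11-21% | 34-48% |
| 2.0 | 0.57-0.69 | 31-43% | 85-97% |

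**4. Growth covariates.** Adding a covariate with partial correlation r, meaning the correlation with the outcome left after prematurity and the other terms, multiplies the residual SD by √(1 − r²). The 75 infants are then worth 75 / (1 − r²).
- r = 0.3: factor 0.95, intervals 5% narrower, worth 82
- r = 0.5: factor 0.87, 13% narrower, worth 100
- r = 0.7: factor 0.71, 29% narrower, worth 147

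**The case against.** The strongest reply has four parts.

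**The error rate is often right, and can err on the safe side.** This stands. With no association, rejection is about 5% for equal exposure spread and in the stratified repeat, and falls to 1-2% if full-term exposure varies more. A reader might infer that infection p-values are generally too small; the protocol does not support that, as it states no spread. There is some reason to expect the inflating direction: the preterm stratum mixes own and donor milk, and section 3.1 says donor milk is lower in fat and protein than early preterm milk. Simulating that mixture gave 5.4-5.9% for a 1 SD gap between the milks and 6.8-8.6% for 3 SD, so the effect is modest. The stratified repeat does not remove the too-small standard errors under a real association.

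**Birth weight and gestational age are not excluded.** This also stands. A reader might infer that they are left out of the growth models. The infant list ends in *etc.*, does not say whether prematurity is yes/no or in weeks, and may be completed in an analysis plan not shown here. The text supports only that they are not named.

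**The precision gain is easily overstated.** It is tempting to apply 1 − r² to the raw correlation of birth weight with later weight. Prematurity is already in the pooled model and the strata are far apart in gestation, so only the remaining correlation counts.

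**The gain from a count model is small.** In one simulated scenario power rose only from 62% to 66%, and negative binomial rejected 3.5% under the null, so it is not exact either. Unequal follow-up is an assumption, since all infants share one six-month schedule. The case for change is valid precision and sensible fitted values rather than power.

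**Conclusion.** The point holds in a limited form. The protocol states an unsuitable method for one outcome, the infection count; this is a stated choice and not detail left for later. Pooled null rejection of about 1% to 9% means that the error rate depends on an exposure pattern the plan neither knows nor controls. The more consistent fault is under a true association, where preterm standard errors are 11-21% too small at a rate ratio of 1.5 per SD and 31-43% too small at 2.0. All of these sizes rest on assumed rates, dispersion and exposure spread. The count problem does not touch weight, length or head circumference.

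The covariate point is secondary. The list is open, and the gap is clearest in the preterm stratum if prematurity is yes/no. How much confounding or lost precision results cannot be determined from the protocol.

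Study II is observational and no formal decision rests on the infection p-value, so this is a worthwhile correction and does not threaten the study.

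**What to change.** In section 3.3.6, separate the count from the growth measures.

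- **Infections and admissions:** negative binomial regression, or Poisson regression with robust standard errors, with log follow-up time as offset if follow-up differs between infants.
- **Growth models:** name gestational age in weeks and the matching birth measure (weight, length or head circumference) as covariates. Say whether prematurity is yes/no or in weeks, and whether age is the mother's or the infant's.

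The cost is a change of wording. Gestational age is needed for eligibility and recovery of birth weight is a study milestone (section 3.3.1), so both should be available; birth length and head circumference should be confirmed. Results for counts become rate ratios instead of mean differences, and the growth models lose one or two degrees of freedom. The full-term stratum may support few covariates: at an assumed mean of 0.3, 25 infants yield 25 × 0.3 = 7.5 expected events, so that count model should be kept small.

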2.3.6. Statistical analysis

Descriptive statistics will be used to present the characteristics of the participating children. Linear regression analyses will be performed with weight and BMI, as well as blood glucose, insulin, A1C, HOMA-IR as dependent variables and physical activity levels, children's and mother's smoking habits, nutritional status including energy intake, consumption of specific food groups and KIDMED score, medical history, genotype and metabolome as the independent variables.

Between Group comparisons for the baseline measurements of the phase II of Study I, will be performed using t-test or Mann-Whitney test, to ensure comparability of the Groups. Then, children

enrolled in the intervention diet will (Group A) be compared to those of the control diet (Group B), regarding their weight and BMI status as well as regarding the glycemic control as indicated by blood glucose, insulin, A1C, HOMA-IR (i.e., primary end points), using Repeated Measures Analysis of Variance (RMANOVA). Moreover, the 2Groups will be compared regarding various cardiometabolic risk factors such as total cholesterol, LDL cholesterol, HDL cholesterol, LDL/HDL cholesterol ratio and triglycerides, improvement in nutritional status including energy intake and consumption of specific food groups, as well as urine biomarkers, biomarkers of intestinal inflammation and microbiome profile, using the aforementioned method. All necessary adjustments (based on the baseline analyses) will be performed to ensure the robustness of the results.

The analyses will be performed by using STATA v15 software (STATA Corp LLL, College Station, TX, USA).

Finally, additional statistical analysis with the view of deriving additional insights and influences in personalised nutrition will be presented in D2.5.

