3.2. Objectives

The objectives of the study are:

- a) to evaluate associations between the mother's diet composition and HM composition in pre- and full-term infants, i.e. how the potential associations between mother's diet and HM nutrient composition is affected by prematurity.
- b) to evaluate the effect of pasteurization/storage on DHM composition.

c) to evaluate associations between HM composition (OMM or DHM) on growth and other health parameters in pre- and full-term infants.

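### Study II names Mann-Whitney and an unspecified t-test for donor-milk values that are paired by batch, so small or moderate changes on pasteurization can be missed

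*Protocol*

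**What the plan says.** Study II objective b (Protocol section 3.2) is "to evaluate the effect of pasteurization/storage on DHM composition".

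Sampling for it is in section 3.3.4.1, under human milk nutrient composition: "DHM aliquots of each milk batch will be collected before and after pasteurization". Under microbiome assessment, the same section says: "OMM and DHM before pasteurization will be analyzed for microorganism's content".

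The analysis is in section 3.3.6. DHM composition, covering both nutrients and microorganism content, "will be compared before and after pasteurization/storage using Student's t-test or Mann-Whitney test". No paired t-test, signed-rank test, or batch or donor term is named anywhere in the document.

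The same two tests appear in section 2.3.6 for the baseline comparison of the two randomized groups of Study I, which "will be performed using t-test or Mann-Whitney test, to ensure comparability of the Groups".

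**The concern.** Two aliquots of one batch share everything that makes that batch differ from others: the donor, the stage of lactation and the donor's diet. The effect of pasteurization is the change within a batch. A test that treats the before and after values as two unrelated samples compares that change with the full spread between batches, which is the wrong yardstick.

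This is the only test that the protocol names for objective b. If the pairing is ignored, a modest but real change in a nutrient or protein may be reported as non-significant, and its confidence interval will be wider than the data justify.

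A second matter concerns the same sentence of section 3.3.6. It compares microorganism content before and after treatment, whereas section 3.3.4.1 names microorganism analysis of DHM for the pre-pasteurization state and does not mention the post-pasteurization state.

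**Working it through.** **The plan's own figure.** There is none for this comparison. The only Study II power statement (section 3.3.5, "In order to achieve statistical power of at least 95% at 5% significance level of two-sided hypotheses") concerns an "evaluation of 10% standardized mean differences of fat and protein composition of HM" with 25 dyads per group. It is not a statement about batches. Whether it is itself achievable is a separate question, and nothing below depends on it.

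**Inputs**
- Structure: one value before and one after per batch (section 3.3.4.1).
- Test: t-test of unstated type, or Mann-Whitney (section 3.3.6).
- Significance level: two-sided 5% (section 3.3.5, carried over).
- Number of batches, n: not given. I assume 25. This borrows the group size from section 3.3.5, which counts dyads and not batches.
- Within-batch correlation, rho: not given. I use a range.

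**Formulas.** With SD s in each state:
- SE assumed by the unpaired test: s × sqrt(2/n)
- Actual SE of the mean change: s × sqrt(2(1 − rho)/n)
- Ratio: 1/sqrt(1 − rho), which is 1.4 at rho 0.5, 2.2 at rho 0.8 and 3.2 at rho 0.9

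The ratio exceeds 1 for every positive rho, whatever n is.

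**Numbers in, n = 25, s = 1.** The unpaired SE is sqrt(2/25) = 0.283. With 48 degrees of freedom the critical t is about 2.01, so the observed change must exceed about 2.01 × 0.283 = 0.569 SD to be significant.
- rho 0.5: the actual SE is sqrt(1/25) = 0.200. A true change of 0.5 SD lies (0.569 − 0.5)/0.200 = 0.34 SE below the threshold, which gives power of roughly 37%. Under no change the threshold is 0.569/0.200 = 2.8 SE away, so the type I error is roughly 0.5%.
- rho 0.8: the actual SE is sqrt(0.4/25) = 0.126. A true change of 0.5 SD lies (0.569 − 0.5)/0.126 = 0.55 SE below the threshold, which gives power of roughly 29%. Under no change the threshold is 4.5 SE away, so the type I error is practically zero.

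**Simulation.** This allows for the SD being estimated (20,000 replicates for the t-tests, 4,000 for Mann-Whitney). Power is for normal data and 25 pairs:

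| True change | rho | Unpaired t | Mann-Whitney | Paired t |
|---|---|---|---|---|
| 0.3 SD | 0.5 | 11% | 10% | 30% |
| 0.3 SD | 0.8 | 4% | 4% | 63% |
| 0.5 SD | 0 | 41% | 38% | 40% |
| 0.5 SD | 0.5 | 38% | 36% | 67% |
| 0.5 SD | 0.8 | 33% | 31% | 97% |
| 0.5 SD | 0.9 | 30% | 31% | 99.9% |

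For a change of 1 SD all three tests have about 92% power or more at every rho examined (0 to 0.95). The unpaired t-test's actual type I error at a nominal 5% is 0.6% at rho 0.5, 0.1% at rho 0.7, and near 0% at rho 0.8 and above.

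**Microorganisms.** Section 3.3.6 needs a value before and a value after. Section 3.3.4.1 names the analysis only for the state before pasteurization. The two passages do not match.

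**The case against.** The best defence is that a paired t-test is also a Student's t-test, and that a sentence about comparing before with after implies pairing. A reader might infer that the protocol has fixed independent-samples tests for both branches. The text does not go that far: the type of t-test is unstated, and its use for independent groups in section 2.3.6 is suggestive only. The defence does not reach Mann-Whitney, which has no matched form; its paired counterpart is the Wilcoxon signed-rank test. Because the protocol names the test, this is also not a detail merely left to an analysis plan.

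It can also be said that the error is conservative, leaves the estimated mean change untouched, and makes false positives rarer. That is correct. A reader might infer that true changes will be missed in general. The calculation does not support this, since changes near 1 SD are found either way.

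The stakes are easily overstated too. Section 3.3.6 announces further analyses in D2.5. In section 3.4 it is the evaluations of the milk that inform the human milk analyzer, and the choice of test does not alter those measurements.

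On microorganisms, a reader might infer that no post-pasteurization data will exist. Section 3.3.4.1 does not say that the analysis is restricted to the earlier state, post-pasteurization aliquots are collected, and the detailed methods sit in deliverables not shown here. What stands is a mismatch in the text.

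**Conclusion.** Section 3.3.6 is wrong as written. Mann-Whitney is invalid for values matched by batch, and the t-test is left open in a way that invites the unpaired version. If pairing is ignored, the test is conservative for any positive within-batch correlation, and small or moderate changes can be missed.

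The direction rests only on positive rho, which is to be expected of two aliquots from one batch. The size is illustrative: 38% against 67% power at rho 0.5, and 33% against 97% at rho 0.8, hold for an assumed 25 batches and a 0.5 SD change. The documents fix none of these three quantities for this comparison.

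The defect is confined to objective b of an observational study and does not touch the randomized comparison in Study I. The microorganism wording in sections 3.3.4.1 and 3.3.6 must be reconciled, but it is not proof that data will be missing.

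**What to change.** In section 3.3.6, replace the two named tests with a paired t-test or a Wilcoxon signed-rank test on the within-batch difference, and report the mean or median change with its 95% CI.

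Section 3.3.4 has donors evaluated each time they donate a batch, so one donor may supply several. In that case use a mixed model with batch nested in donor in place of the simple paired test, which cannot carry a donor term. A donor effect on level cancels out of a within-batch difference, so the model should let the change itself vary by donor.

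For microorganism content, either state that post-pasteurization aliquots are analysed, if that is already planned, or drop microorganism content from the before/after comparison.

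The cost is a sentence or two of analysis text. Nutrients need no new samples, because both aliquots are already collected. Dropping microorganisms from the comparison costs nothing; adding a post-pasteurization analysis that is not yet planned would mean extra laboratory work.

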3.3.4. Observational Study Phase

[figure not shown]
A thorough evaluation of the health status of the mother-infant dyad and the donors providing the DHM will be performed, including dietary and other lifestyle parameters assessment, medical history and evaluation, anthropometric measurements and microbiome profiling. A description of each of these aspects follows. Evaluations in the donors providing the DHM will be performed every time a batch is donated. Detailed Standard Operating Procedures employed for sample collection, storage and outcome assessment will be provided in WP3. Results obtained from data analysis will be used to feed the NUTRISHIELD platform and train the NUTRISHIELD algorithm.

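### Study II matches donor-milk aliquots by batch, but the tests named for the before/after comparison do not use the pairing, so small to moderate processing losses may be missed if batches are few

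*Protocol*

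**What the plan says.** Objective (b) of Study II (Protocol, section 3.2) is "to evaluate the effect of pasteurization/storage on DHM composition". For sampling, section 3.3.4.1 states: "DHM aliquots of each milk batch will be collected before and after pasteurization". Section 3.3.4 adds: "Evaluations in the donors providing the DHM will be performed every time a batch is donated", so one donor may supply several batches.

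The analysis given in section 3.3.6 is that the nutrient and microorganism content of DHM "will be compared before and after pasteurization/storage using Student's t-test or Mann-Whitney test". It mentions no paired test, batch term or donor term.

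Study I (section 2.3.6) uses the same two tests for the baseline comparison of its two randomized groups, which "will be performed using t-test or Mann-Whitney test, to ensure comparability of the Groups".

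On microorganisms, section 3.3.4.1 says only: "OMM and DHM before pasteurization will be analyzed for microorganism's content".

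**The concern.** Two aliquots of one batch are the same milk at two processing stages. Much of the difference between batches (donor, stage of lactation, diet) is common to both and cancels in the within-batch difference. A test for independent samples does not remove this shared variation. It stays in the error term, and the test treats the aliquots as if they came from unrelated batches.

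This is not a detail left open for a later analysis plan. The protocol names tests, and at least one of them does not fit the protocol's own sampling. The comparison is the only analysis that section 3.3.6 gives for objective (b). Section 3.4 says that these evaluations will provide input to the human milk analyzer, with a focus on proteins that may change on heating. At stake is whether modest changes are recognized and how precisely they are estimated.

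**Working it through.** **Figures in the plan.** There is no figure to reproduce for this comparison. The 25 per group in section 3.3.5 counts mother-infant dyads, not milk batches. No number of batches, within-batch correlation or expected loss is given, so all three are assumptions here, shown over a range.

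**Standard error.** Let n be the number of batches, s the SD at each stage (taken as equal) and rho the within-batch correlation.

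- Independent-sample formula: SE = s·sqrt(2/n).
- Correct for pairs: SE = s·sqrt(2(1-rho)/n).
- Ratio: 1/sqrt(1-rho). This is 1/sqrt(0.5) = 1.41 at rho 0.5, 1/sqrt(0.2) = 2.24 at rho 0.8 and 1/sqrt(0.1) = 3.16 at rho 0.9.

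The ratio does not depend on n or on the size of the loss. With complete pairs the estimated mean change is the same either way; only its standard error, interval and test differ.

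**Type I error.** Simulated paired normal data with no true change, 25 batches, nominal two-sided 5%: the independent t-test rejects in about 0.7% at rho 0.5, and in 0.1% or less from rho 0.7.

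**Power.** Two-sided 5%, loss d in units of the between-batch SD. Paired power comes from the noncentral t with noncentrality d·sqrt(n)/sqrt(2(1-rho)). For example, n = 25, d = 0.3 and rho = 0.8 give 0.3 × 5/sqrt(0.4) = 2.37, and power 62%. Power of the independent t-test comes from simulation. Each cell shows independent vs paired:

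| Batches (assumed) | Loss | rho 0.5 | rho 0.8 | rho 0.9 |
|---|---|---|---|---|
| 25 | 0.3 SD | 10% vs 30% | 3.5% vs 62% | 1% vs 90% |
| 25 | 0.5 SD | 38% vs 67% | 33% vs 97% | 30% vs 100% |
| 25 | 0.8 SD | 87% vs 97% | 95% vs 100% | 98% vs 100% |
| 50 | 0.5 SD | 76% vs 93% | 86% vs 100% | 92% vs 100% |
| 100 | 0.5 SD | 98% vs 100% | 100% vs 100% | 100% vs 100% |

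The rank tests behave in the same way. With 25 batches and a 0.5 SD loss, Mann-Whitney vs signed-rank gives 35% vs 65% at rho 0.5, 33% vs 96% at 0.8 and 27% vs 100% at 0.9.

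**Which form of t-test is meant.** Section 3.3.6 does not say. Two things point to the two-sample form: its stated alternative is Mann-Whitney rather than the signed-rank test, and section 2.3.6 uses the same two tests for independent groups.

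**Microorganism content.** Section 3.3.6 plans a before/after comparison, but section 3.3.4.1 lists microorganism analysis of DHM only before pasteurization. As written, this endpoint has no after value to pair.

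**The case against.** The strongest reply has four parts.

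- *The t-test may be meant as paired.* This is possible, since the term covers both forms. The two-sample reading is a strong inference, not an explicit statement. But Mann-Whitney cannot be read as paired, so the non-parametric option is wrong on any reading.
- *The planned test is not blind to real losses.* This stands. A reader might infer that real processing losses will be reported as no change. The documents do not support that: they give no batch count, correlation or expected loss, and the table shows that larger losses, or moderate losses with many batches, are found by either test. Batches could well exceed 25, because donors are evaluated at each donation.
- *The error is conservative and leaves the estimate unchanged.* Also true. With positive rho it creates no excess of false positives, and what passes to the analyzer work need not be a p-value. The confidence intervals are still too wide whatever the loss.
- *Other documents may carry the detail.* Section 3.3.6 refers additional analysis to D2.5, section 3.3.4.1 refers the milk protocol to Deliverable 2.3, and Figure 3.2 is not visible. It therefore cannot be said that no other analysis of objective (b) exists. But a further analysis would not make the tests named here fit the data.

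**Conclusion.** The point holds in a limited form. Batch-matched aliquots are assigned an independent-sample rank test and a t-test that is not called paired and is probably the two-sample one. If the pairing is ignored and rho is positive, the standard error is inflated by 1/sqrt(1-rho), intervals are too wide and the test runs well below its nominal 5%. Losses of about 0.3 to 0.5 SD are likely to be missed if batches are few. Losses of about 0.8 SD or more, or 0.5 SD with about 100 batches, would still mostly be detected.

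The power figures rest on assumed batch counts, assumed rho, equal SDs and normal data. A positive rho is itself an assumption, though a natural one for two aliquots of the same milk. The mismatch between sampling and test needs none of the numerical assumptions.

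**What to change.** In section 3.3.6, replace the sentence on the DHM comparison with, for example: *For each constituent, the within-batch difference (or log ratio, for positive concentrations where suitable) will be tested with the paired t-test or the Wilcoxon signed-rank test and reported as the mean change with its 95% confidence interval. Where a donor contributes more than one batch, a mixed model with a donor random effect will be used.* Keep the batch ID on both aliquots.

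For microorganism content, first reconcile section 3.3.6 with section 3.3.4.1: either state that milk after pasteurization is also analyzed, or drop that endpoint from the before/after comparison. If counts after pasteurization are taken, the analysis must allow for zeros, because a log ratio is then undefined.

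For the constituents already sampled at both stages, the cost is a sentence or two and a label, with no new samples. Measuring microorganisms after pasteurization would add laboratory work if it is not already planned.
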